**Identifiers: NCT04227236**

**Unique Protocol ID: 1R41HD094406**

**Brief Title: Interventions to Improve Reproductive Health Among Adolescents**

**Document date: October 30, 2023**

## STUDY PROTOCOL

To address the need for a facilitator training that was cost-effective, easily accessible, and delivers the MPC content with the same effectiveness as the currently available in-person training, we developed and tested a prototype of an online simulator-based training for facilitators of MPC using a mixed method approach of survey assessments and teacher observations. Using a randomized controlled trial for the pilot test of the prototype, we randomly assigned a convenience sample of 53 adults to receive either online simulation training or in-person training for one activity within the MPC program. Using non-inferiority analysis (Schumi & Wittes, 2011), a statistical technique that specifically tests for similarity between groups, we hypothesized that participants who received the online simulation training would perform no worse than the in-person group on knowledge, self-efficacy, fidelity and quality of instruction via self-report survey and teacher observations. We also examined the self-reported acceptability, usability/applicability, likability and overall impressions among the online simulation group.

### **Making Proud Choices Prototype**

To assess feasibility of using a simulated training environment to train educators to address the challenges of a skills-based sexual health curriculum such as MPC, the prototype focused on the content from one activity, the “Condom Line-Up”, which is one component of the “Developing Condom Use and Negotiation Skills” module. According to the developer, this activity is highly interactive, relying on the facilitator’s skill in processing student comments in a sensitive and constructive manner, as well as sensitive in nature (i.e., focusing on the use of condoms for adolescents). These qualities made the activity a good choice for this “proof of concept” phase. The in-person version of the training lasted approximately 25 minutes. The online version was comparable in length and included three elements: a) Didactic training: facing the learner, a master trainer avatar provides the rationale, learning objectives and goals for the activity; b) demonstration which entailed a virtual facilitator teaching the topic and virtual youth having typical reactions and responses, in a side-view of a classroom; and c) simulation teach-back: the view switches to the point of view of the learner, with the learner playing the role of the facilitator. For instance, a scene starts in which the virtual facilitator begins to teach to the virtual youth. Throughout the module, the scene pauses (at approximately 20 spots), and the learner is given at least 4 options on what action to take next. Although a best option exists, all options have some elements of better and worse responses. After the learner chooses an option, written text appears providing feedback about the option chosen. Learners are encouraged to go back and see how the class reacts if they had chosen other options as a way to maximize learning. Compared to many traditional online trainings that are unable to simulate the true give-and-take of a classroom environment, this innovative technology allows for the closest approximation to the feedback received from in-person training. Further, this approach can better reinforce information than in-person training in which there is no opportunity to witness the myriad of youth reactions.

### **Participants**

In 2017, participants (those who represent potential MPC facilitators) were recruited to be a part of the pilot test using a combination of flyers posted at local universities and online advertisements (e.g., Craigslist, Facebook). Two-hundred forty-seven individuals expressed interest in the study, 93 of whom were excluded because they were younger than 21 years of age or had prior experience with MPC or providing other STI or pregnancy prevention education. Out of the 154 eligible individuals, the research team reached 123, and using a random number generator, randomly assigned 62 individuals who agreed to participate to either the online simulation (31 participants) or in-person (31 participants) training. Ultimately, 53 attended the day of pilot test (31 online simulation and 22 in-person). All participants

received one hundred dollars for participation in the pilot study. All participants provided written informed consent. All study procedures were reviewed and approved by RAND Corporation's Institutional Review Board (IRB).

### **Training and Fidelity Observations**

All trainings occurred at the same facility, run by staff with extensive experience training MPC facilitators from a variety of backgrounds. Both the simulation-based and in-person groups were trained on the same Condom Line-Up activity. Participants in the simulation-based training group completed the training individually at their own pace as they would in real-world practice (average time = 31 minutes). The self-paced approach allowed participants to take as much time as they preferred to review and practice the lessons, as well as an opportunity to complete tasks multiple times if desired. Participants in the in-person training group received trainings led by a trainer with extensive experience training MPC facilitators. In-person trainings were offered to groups of 4-8 participants each; these were 20-minute sessions with an additional 5-minutes for Q&A following the training. The in-person approach allowed participants the opportunity to hear other participants' questions and the trainer's responses, providing the opportunity to think about questions that they may otherwise not have considered. All participants completed pre- and post-training surveys. Following the post-survey, each participant completed a demonstration teaching where they conducted the Condom Line-Up activity from start to finish to a group of staff trained to emulate teens and provide scripted responses during the session. Each participant was videotaped for the demonstration teaching.

### **Measures**

Pre- and post-training surveys assessed knowledge, self-efficacy, facilitator skills, and beliefs and impressions related to the use of the online prototype. Observation measures focused on fidelity to curriculum for the Condom Line-Up activity and quality of the instruction.

#### **Demographics**

Participants provided demographic information on race/ethnicity, age, gender, education, and experience working with youth and teaching HIV/STI programs.

#### **Facilitator Knowledge**

Knowledge of the curriculum (objective and rationale of the Condom Line-Up) and knowledge of the steps of proper condom use was assessed using three items informed by the MPC curriculum (e.g., To the best of your ability, please select the rationale for engaging students in an activity that shows them the proper steps for using condoms safely.). Responses were coded as correct or incorrect. We examined each knowledge item individually in the analyses.

#### **Facilitator Self-efficacy**

Self-efficacy of teaching sexual health education was assessed using three questions (e.g., How confident are you that you can teach teens how to correctly use condoms?) rated from 1 (not at all) to 7 (extremely). We created a self-efficacy scale score by averaging the scores of the three items for each participant ( $\alpha = .93$  for pre-test and  $\alpha = .94$  for post-test).

#### **Facilitator Skills**

Participants responded to four open ended questions assessing facilitator skills related to handling sensitive questions, creating a safe and inclusive environment, engaging students, and handling whispering during a presentation on proper condom use. For example, participants responded to the following scenario: [You are preparing to teach a class of high school students about safe condom use strategies. A student raises their hand and says "Why do we all have to do this? Some people here believe in waiting till marriage to have sex." Another student then shouts out "Virgin!" and the class laughs. What do you do?] The purpose of these open-ended questions was to present participants with typical scenarios, ask for an open-ended answer (as opposed to choosing from a list of possible responses), and then rate their answer. Two independent coders (blinded to condition), who were trained by a senior researcher on the team, rated the videotaped responses as 2 for "done correctly," 1 for "done partially correct" and 0 for "not done correctly." The intraclass correlation coefficient (Cicchetti, 1994) was .76 for the pre-survey

responses and .79 for post-survey responses.

### ***Beliefs and Impressions of the Prototype***

Participants from the online simulation group also responded to questions assessing their perceived acceptability, applicability, liking, and overall impressions of the training. In addition to assessing the impact of the simulated training environment on learning the material, it is important to determine what potential teachers think about the simulation as this would likely influence its adoption into schools (Khlaif, 2018). To assess acceptability, participants rated 19 items on a scale of 1 (strongly disagree) to 7 (strongly agree) from the Post-Study System Usability Questionnaire (PSSUQ) (Lewis, 1995), a well-known, valid and reliable ( $\alpha = .91$  or higher) measure that assesses perceptions of the technical aspects of computer-based systems and programs (e.g., system usefulness, information quality, and interface quality). To assess usability and applicability to teaching youth about sexual health and safety, participants completed the Moore and Benbasat (1991) measure of factors that predict adoption of a new technology, specifically, relative advantage (e.g., "Using the online training would make my job easier."), compatibility (e.g., "The online training fits into my work"), ease of use, and result demonstrability (e.g., "I could talk to others about the consequences of using the online training"). Wording was adapted to be relevant to the online simulation training. Items were rated on a scale ranging from 1 (strongly disagree) to 7 (strongly agree) ( $\alpha = .96$ ). Participants rated likability with one item: [On a scale of 1 to 7, with 1 being disliked it very much and 7 being liked it very much, how much did you like the appearance of the Condom Line-Up e-training overall—the colors, the pictures, the buttons, etc.?]

Finally, participants' overall impressions of the training were assessed using a 4-item measure, rated on a 7-point Likert-scale (very difficult to use to very easy to use, very boring to very interesting, very amateurish to very professional, and very basic to very informative). Items were averaged to create an overall impression score (Cronbach alpha = .90)

### ***Fidelity and Quality of Instruction***

Each of the nine components from the Condom Line-Up were rated independently by two coders from the videotapes as 2 for "done correctly," 1 for "done partially correct" and 0 for "not done correctly." Coders received training on coding rules from a senior researcher on the team and one of the MPC training developers. Coders practiced the coding scheme on a subset of subjects in a group format where coders rated alongside a senior researcher on the team. Coder disagreement (>1-point difference) was discussed with the measure developer to reach a consensus. After training, two coders rated sub-activities of all the remaining 45 subjects. Inter-rater reliability using intra-class correlations (ICC) (Cicchetti, 1994) ranged from .78 to .98, all within the good-excellent range. Final scores were calculated as the average of the two coders' ratings.

## **STATISTICAL ANALYSIS PLAN (SAP)**

First, we performed  $\chi^2$  tests and  $t$  tests to assess whether the two groups differed on demographic and background variables, and pre-test scores on knowledge, self-efficacy and facilitator skills. Second, we examined the non-inferiority of online simulation to in-person by comparing two groups in post-training knowledge, pre-post change in self-efficacy and facilitator skills, and post-training scores of fidelity and quality of instruction. Non-inferiority analyses assess whether a new treatment or approach (e.g., online simulation) is acceptably efficacious as an existing approach (i.e., in-person training) (Althunian et al., 2017). Or, in other words, the new approach or treatment is not less effective than the existing approach by more than a small pre-specified amount. This amount is known as the non-inferiority margin.

To test non-inferiority of the online simulation training, we constructed a two-sided 95% confidence interval (CI) for the difference between online simulation and in-person (computed as in-person minus online simulation) for: (a) change in percent correct for knowledge of the curriculum (objective and rationale of the Condom Line-Up) and knowledge of the steps of proper condom use, both computed as post-test minus pre-test, using the method described in Farrington and Manning (1990), (b)

change in self-efficacy and facilitator skills (computed as post-test minus pre-test) using *t*-test statistic, and (c) scores of fidelity and quality of instruction based on the role-play activity after the trainings using the *t*-test statistic (Table 5). Non-inferiority of online simulation to in-person (meaning the online simulation group was no worse than the in-person group) could be claimed if the upper bound of the CI of the difference was less than the margin of non-inferiority. Based on standard practice (e.g., Schoneveld et al., 2018) and consensus among the developers of the MPC training on an acceptable difference between in-person and online simulation scores, the non-inferiority margin was set at 5% for percent correct of knowledge items, 0.5 *SD* of the in-person change in self-efficacy and facilitator skills, and 0.5 *SD* of the in-person scores of fidelity and quality of instruction. All tests were performed in SAS 9.4. (SAS Institute, 2013)

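### Fidelity and quality of instruction have no pre-test and are compared unadjusted, although experience working with youth is recorded; adjusting for it would add some precision and guard against imbalance from unequal attendance

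*Combined protocol and SAP*

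**What the plan says.** The Participants section excluded people who were "younger than 21 years of age or had prior experience with MPC or providing other STI or pregnancy prevention education". General work with young people, such as classroom teaching or camp leadership, is not an exclusion. The Demographics section lists "experience working with youth and teaching HIV/STI programs" among the recorded variables but does not say how it was coded.

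Fidelity and quality come from one videotaped lesson taught after training. Training and Fidelity Observations states: "Following the post-survey, each participant completed a demonstration teaching". No equivalent lesson was taught before training.

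The SAP first runs chi-square and t tests "to assess whether the two groups differed on demographic and background variables". It attaches no consequence to the result. It then builds a "two-sided 95% confidence interval (CI) for the difference between online simulation and in-person", computed as in-person minus online. For item (c), the "scores of fidelity and quality of instruction based on the role-play activity after the trainings", this is a t interval with no covariate, and its upper bound is compared with 0.5 SD of the in-person scores. For self-efficacy and facilitator skills, item (b) uses change from pre-test.

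The Participants section reports 31 people randomised to each arm by random number generator, with no stratification mentioned. On the day, 31 online and 22 in-person participants attended.

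**The concern.** Item (c) covers the trial's only directly observed teaching. Starting ability cannot be subtracted out, as it is in item (b). Someone used to managing groups of teenagers may well teach a better demonstration lesson whichever training they received. The trial recorded a variable bearing on this and leaves it out of the comparison.

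Two things are at stake. The first is precision: variation explained by youth experience stays in the error term, so the interval is wider than it need be. The second is comparability: none of 31 online but 9 of 31 in-person participants failed to attend, so the groups compared are not the groups randomised. If attendance was related to youth experience, the difference would be systematic and the planned interval would not allow for it. It could favour either arm.

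**Working it through.** **Inputs from the documents.** 31 online and 22 in-person; two-sided 95% interval; margin 0.5 SD of the in-person scores. The plan states no power or target sample size, so there is no design figure to reproduce.

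**Assumptions not in the documents.** Half of participants have youth experience. It raises the score by 0.3, 0.5, 0.8 or 1.2 SD, where the SD is that among people with the same experience (set to 1). SDs are equal across arms. All 53 attenders are scored.

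**Precision as planned.** SE = √(1/31 + 1/22) = 0.279 SD. Half-width = 2.008 × 0.279 = 0.560 SD. This exceeds the 0.5 SD margin, so a claim needs online to be ahead by about 0.06 SD in the sample. The chance of a claim when the trainings are equal is about 42% by noncentral t, and about 41% by simulation with the margin set from the observed in-person SD.

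**What adjustment can gain.** At 50% prevalence the share of variance explained is R² = 0.25e²/(1 + 0.25e²) for effect e. The half-width shrinks by about √(1 − R²), before a small loss from chance differences in the covariate.

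| Effect e | R² | √(1 − R²) | Correct claim, unadjusted | Correct claim, adjusted |
|---|---|---|---|---|
| 0.3 | 0.0225/1.0225 = 2.2% | 0.99 | 41% | 41–42% |
| 0.5 | 0.0625/1.0625 = 5.9% | 0.97 | 41% | 43% |
| 0.8 | 0.16/1.16 = 13.8% | 0.93 | 41% | 46% |
| 1.2 | 0.36/1.36 = 26.5% | 0.86 | 41% | 52% |

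The last two columns are simulated (20,000 or more runs per scenario).

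**Error rate under intact randomisation.** With the same prevalence in both arms and online truly inferior by the margin, simulated false-claim rates are about 2.3–2.5% unadjusted and 2.3–2.6% adjusted. Neither analysis has an advantage here.

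**Error rate given an imbalance favouring online.** Let the expected share with experience be 60% online and 40% in-person. The shift is 0.20 × e. The in-person SD is √(1 + 0.24e²), because 0.4 × 0.6 = 0.24, and the margin is half of that.

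| Effect e | Shift | Margin | Shift/margin | False claim, unadjusted | False claim, adjusted |
|---|---|---|---|---|---|
| 0.3 | 0.06 | 0.505 | 12% | about 4% | 2.2–2.4% |
| 0.5 | 0.10 | 0.515 | 19% | about 5% | 2.2–2.4% |
| 0.8 | 0.16 | 0.537 | 30% | about 7% | 2.2–2.4% |
| 1.2 | 0.24 | 0.580 | 41% | about 11% | 2.2–2.4% |

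If the same 20-point difference favoured in-person, the chance of a correct claim under equal training would fall from 42% to about 34%, 29% and 22% for effects of 0.3, 0.5 and 0.8 SD (noncentral t, with the margin held at 0.5).

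**How often chance alone does this.** Exact binomial enumeration at 50% prevalence gives a gap of 20 points or more in either direction 15.2% of the time. In the direction that favours online it is half that, 7.6%.

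**Whether the baseline test would catch it.** Of the chance gaps of 20 points or more, 66% are non-significant at 5%. For a true 60% v 40% split the test has about 30% power.

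**Attendance.** Losses are 0/31 online and 9/31 = 29% in-person.

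**The case against.** The strongest reply is that an unadjusted comparison after randomisation is valid, because its interval already allows for chance differences in any covariate. This stands, and the simulated error rates confirm it. A reader might infer that leaving out youth experience raises the trial's false-claim rate above 2.5%. The documents do not support that: the 4–11% figures hold only given a fixed difference favouring online, which randomisation does not produce on average.

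The effect size can also be questioned, and this too stands. Fidelity is scored on nine specified components, the acting teens gave scripted responses, and people with the most relevant teaching experience were excluded. General youth work may matter less for fidelity than for quality of instruction, and at 0.3 SD adjustment gains almost nothing. Low power here is mainly a matter of sample size, which a covariate cannot cure.

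Other covariates, such as pre-test facilitator skills or self-efficacy, could also stand in for starting ability. The SAP is written in the past tense, so a newly chosen covariate may well be post hoc.

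The appeal to randomisation does not dispose of unequal attendance, because the groups analysed are no longer those randomised. Nor does the planned baseline test protect against imbalance, given its low power and the absence of any rule linking it to item (c).

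**Conclusion.** The planned analysis of item (c) is valid under intact randomisation but omits a recorded and plausibly prognostic covariate for outcomes that have no pre-test. The certain part of the benefit is modest: the chance of a correct claim under equal training rises by roughly 2 to 5 percentage points for effects of 0.5–0.8 SD, with almost nothing at 0.3 SD and about 11 points at 1.2 SD. The conditional part is protection against measured imbalance, which matters because in-person attendance was 71% (22/31) against 100% online.

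The documents do not show that the arms differed on youth experience, or that the non-inferiority conclusion is biased. Prevalence and effect are assumptions, and all 53 attenders are taken as scored. On that last point, Fidelity and Quality of Instruction describes ratings of 45 participants after coder training and does not say how the others entered the analysis.

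**What to change.** For each outcome in item (c), add a linear model with arm and the recorded youth-experience variable. Take the 95% interval for in-person minus online from it and compare the upper bound with the same margin, 0.5 SD of the in-person scores (the raw SD, not the residual SD). Include the covariate whatever the baseline test shows, and state how it was coded. Show the planned t interval beside it. Label the adjusted analysis post hoc if results are already known. Report youth experience by arm for those who attended, and for the non-attenders if it was recorded.

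The cost is one extra model per outcome on data already collected, one degree of freedom and possibly the post hoc label. The model corrects measured imbalance only and does not recover the nine non-attenders.

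### Is a margin of 0.5 SD of in-person change unsafe because it is not tied to how much in-person training improves scores?

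*Combined protocol and SAP*

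**What the plan says.** The Statistical Analysis Plan compares pre-post change in self-efficacy and facilitator skills between arms, as in-person minus online. Non-inferiority is claimed if the upper limit of the two-sided 95% confidence interval is below the margin, which for these outcomes is 0.5 SD "of the in-person change in self-efficacy and facilitator skills". The basis given is one sentence covering every margin, including the 5% margin for the knowledge items: it opens "Based on standard practice" and adds "consensus among the developers of the MPC training on an acceptable difference between in-person and online simulation scores".

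The Study Protocol section describes the need as a training that "delivers the MPC content with the same effectiveness as the currently available in-person training". The hypothesis in the same section is narrower: that the online group does not do worse than the in-person group. The Participants section reports 53 attenders, 31 online and 22 in-person. There is no untrained arm. On data, Training and Fidelity Observations states: "All participants completed pre- and post-training surveys". Fidelity and quality have no pre-measure; the SAP analyses "scores of fidelity and quality of instruction based on the role-play activity after the trainings".

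**The concern.** An SD of change measures how much people differ in their change. It does not measure how much the training helps. A non-inferiority margin is easiest to interpret when it is smaller than the benefit of the comparator, because meeting it then implies that some benefit was kept. Here nothing links the two. The documents give no expected or past in-person gain, no share of it that must be kept, and no condition that either arm improves.

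If in-person training lifts self-efficacy or skills by less than half an SD of change, a training with no effect satisfies the margin. A reader who took the verdict as evidence of equal effectiveness could then be misled. The knowledge items share the feature: if the in-person gain is under 5 percentage points, an online arm with no gain lies inside the 5% margin.

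**Working it through.** **Inputs from the documents.** n = 22 in-person and 31 online; margin 0.5 × in-person SD of change; two-sided 95% interval; t statistic. The documents state no power, gain or SD of change, so there is no plan figure to reproduce.

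**Assumed.** True in-person gain g, in units of the in-person SD of change, from 0.1 to 1.0; normal change scores; equal SDs unless stated; pooled t.

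**Share of the in-person gain kept at the margin** = 1 − 0.5/g:
- g = 0.4: 1 − 1.25 = −25%
- g = 0.5: 0%
- g = 0.8: 1 − 0.625 = 37.5%
- g = 1.0: 50%

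So a zero-gain online training is inside the margin exactly when g is below 0.5.

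**Precision.** SE = √(1/22 + 1/31) = 0.279 SD. Half-width = 2.008 × 0.279 = 0.56 SD. To pass, the online arm must look better than in-person by about 0.56 − 0.50 = 0.06 SD.

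**How often the rule declares non-inferiority, and the effect of an added gate.** The gate considered is that the lower 95% limit of the online arm's own mean change must exceed zero. With 31 online participants, the observed online gain must then exceed t(0.975, 30)/√31 = 2.04/5.57 = 0.37 SD. Results are from simulation with 400,000 trials per scenario; each cell shows the rule alone / the rule plus the gate.

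| In-person training effect (SD) | Online gain 0 | Online effect 0, plus 0.2 SD retest lift in both arms | Both arms gain equally (no retest lift) |
|---|---|---|---|
| 0.1 | 28.3% / 2.2% | 28.3% / 12.6% | 41.3% / 7.0% |
| 0.2 | 17.8% / 2.0% | 17.8% / 9.4% | 41.2% / 15.2% |
| 0.3 | 10.1% / 1.5% | 10.1% / 6.3% | 41.2% / 25.5% |
| 0.4 | 5.2% / 1.1% | 5.3% / 3.7% | 41.3% / 34.2% |
| 0.5 | 2.4% / 0.7% | not run | 41.3% / 39.1% |

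With zero online gain and an in-person gain of 0.8 SD, the rule alone passes in about 0.1% of trials. If the online SD is 0.8 or 1.25 times the in-person SD, the first-column rate for the rule alone is 35.1% or 21.7% at 0.1 SD, and 6.3% or 4.2% at 0.4 SD.

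**The other possible repair: a margin that keeps half the in-person gain (0.5g).** For 80% power at one-sided 0.025 and no true difference, n per arm = 2(1.96 + 0.84)²/(0.5g)², about 62.8/g². This gives 1570 at g = 0.2, 393 at 0.4, 252 at 0.5, 99 at 0.8 and 63 at 1.0. At g = 1.0 that margin equals the plan's own 0.5 SD. At smaller gains it is out of reach for a pilot of 53.

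**The case for a change.** The case for acting is that the arithmetic is sound and the data already exist. Rating error widens the spread of change and hence the raw margin; inter-rater agreement for the skills responses was .76 and .79. Small numbers hide the weakness: with 200 per arm and an in-person gain of 0.2 SD, a zero-gain online training would pass 84% of the time. A check on the online arm's own gain needs only one more confidence interval per outcome and, without a retest effect, cuts the 28% to about 2%.

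The conditional arithmetic stands, and so does the warning for any larger trial that takes over this margin. The gate does not.
- It tests the online arm, although the missing link is between the margin and the in-person gain.
- It cannot tell learning from retest. With an assumed 0.2 SD retest lift, 28% falls only to 13%.
- It costs most where the concern is greatest: two equally effective trainings that each gain 0.1 SD would see the chance of a full claim drop from 41% to 7%.
- Recruitment was in 2017, the SAP is written in the past tense and the document is dated October 2023, so a new success condition would be post hoc.

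**Conclusion.** No change to the plan follows. Agreement among the developers on a tolerable loss is a recognised kind of basis for a margin, and the rule answers the relative question that the hypothesis asks. If the in-person gain is below 0.5 SD, a zero-gain online arm truly is within the stated margin. The 28% to 5% are therefore not false-positive rates of the rule; they show how little a relative verdict says about absolute benefit. The aim of equal effectiveness describes the need behind the work and is not the decision criterion.

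The condition is also unshown. No section gives a gain or an SD of change. Participants had no earlier experience with this curriculum or with similar prevention teaching, so gains may well be large, and at 0.8 SD the issue all but disappears.

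What remains is reporting that analysts would ordinarily supply: each arm's pre-post change with its 95% interval beside the margin, and conclusions worded as relative to in-person training, including those for fidelity and quality. The SAP refers to a Table 5 that is not in the supplied text and may already hold those figures. None of this alters a result. The figures rest on assumed gains, normal change scores and 22 and 31 analysed participants.
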